## Statistical Analysis Plan

The tables will be sorted by overall descending frequency of SOC and then, within a SOC, by overall descending frequency of PT based on the patient count for the total column. If only event count is presented, the sorting will be done based on the event count.

In addition, selected AE tables will be broken down by treatment/study group.

### 9.5. LABORATORY EVALUATIONS

Laboratory samples for hematology and clinical chemistry will be analyzed by a central laboratory (located in the United States of America) to ensure consistent interpretation of results. In the event of an unexplained clinically significant abnormal laboratory test value, the test should be repeated immediately and followed up until it has returned to the normal range and/or an adequate explanation of the abnormality is found.

All parameters will be converted to consistent units according to the International System of Units (SI) before summarization. The following will be summarized by treatment group and overall:

- Actual values and change from baseline, if applicable, at each visit for each parameter (for handling of data from the ET visit, see [Section 6.4](#))
- Number and percentage of patients with normal or “abnormal” (i.e., out of reference range) labs at each visit for each parameter
- Number and percentage of patients with potentially clinically significant (PCS) lab values at each visit for each parameter
- Number and percentage of patients with potentially clinically significant changes (PCSC) in lab values at each post-baseline visit for each parameter

PCS and PCSC will be identified for specific laboratory parameters as outlined in the following table.

Laboratory Parameter	Units	Criteria for PCS Values (Actual values)		Criteria for PCSC values (Changes from baseline values)	
		High	Low	% increase	% decrease
Hemoglobin	g/L	> 10 above ULN	>20 below LLN	NA	25%
Hematocrit	L/L	>0.04 above ULN	>0.05 below LLN	NA	25%
WBC	GI/L	>5 above ULN	>1 below LLN	100%	50%
Neutrophils	GI/L	NA	<0.5xLLN	100%	50%
Neutrophils	%	NA	<0.5xLLN	100%	50%
Lymphocytes	GI/L	NA	<0.5xLLN	100%	50%
Lymphocytes	%	NA	<0.5xLLN	100%	50%

## Statistical Analysis Plan

Total bilirubin	µmol/L	>1.5xULN	NA	300%	NA
Total protein	g/L	>15 above ULN	>15 below LLN	200%	60%
Albumin	g/L	>5 above ULN	>5 below LLN	NA	60%
AST	U/L	>3xULN	NA	300%	NA
ALT	U/L	>3xULN	NA	300%	NA
Alkaline Phosphatase	U/L	>3xULN	NA	300%	NA
GGT	U/L	>3xULN	NA	300%	NA
Creatinine	µmol/L	>1.5xULN	NA	200%	NA
Urea	mmol/L	>2.5xULN	NA	300%	NA
Uric Acid	µmol/L	>3xULN	NA	300%	NA
Sodium	mmol/L	>5 above ULN	>5 below LLN	10%	10%
Potassium	mmol/L	>1 above ULN	>0.5 below LLN	25%	20%
Carbon dioxide	mmol/L	>40	<16	25%	25%
Calcium	mmol/L	>2.99	<1.78	30%	30%
Glucose (fasting)*	mmol/L	>11.1	<2.8	300%	40%

ULN = Upper limit of normal range, LLN = Lower limit of normal range

Baseline is defined as the last non-missing assessment before the first dose of CVT-301 in study CVT-301-004 for the patients who received CVT-301 in CVT-301-004 and as the last non-missing assessment before the first dose of CVT-301 in CVT-301-004E for the rest of the patients. ' \* fasting defined as ≥4 hr from prior meal

The tables showing the normal/abnormal values, PCS values and PCSCs will be done both as summaries of all data and as shift tables (i.e., classified by the baseline status).

Values which fall outside the central laboratory normal range will be flagged as “L” - below normal range, or “H” - above normal range, on the data listings. PCS and PCSC values will also be flagged. All repeated values will be presented on the data listings but not included in the summaries showing data by visit.

### 9.6. VITAL SIGNS

Standard vital sign measurements will include RR, systolic and diastolic BP (SBP, DBP), and HR. At SV1 (or SV2) and each of the subsequent study visits, and in the event of a clinically significant finding that could be suggestive of symptomatic orthostatic hypotension (e.g., dizziness, lightheadedness, or other AE), orthostatic vital signs will be performed. Orthostatic vital sign measurements will include SBP, DBP, and HR.

The following will be summarized:

- Change from baseline to other visit pre-dose values for each parameter. Baseline is defined as the last non-missing assessment before the first dose of CVT-301 in study CVT-301-004 for the patients who received CVT-301 in CVT-301-004 and as the last non-missing assessment before the first dose of CVT-301 in CVT-301-004E for the rest of the patients. '

## Statistical Analysis Plan

- Actual values and change from pre-dose to post-dose time points at TV1 by time point for each parameter
- Number and percentage of patients with PCS values at each applicable visit and time point for each standard vital sign parameter
- Number and percentage of patients with PCSC values at each applicable visit and time point for each standard vital sign parameter
- Number and percentage of patients with Orthostatic hypotension at each applicable visit

PCS and PCSC for standard vital sign will be identified as outlined in the following table.

Vital Sign	Units	Criteria for PCS Values (Actual values)		Criteria for PCSC values (Change from Baseline or pre-dose values *)	
		High	Low	increase	decrease
Pulse rate	bpm	>120	<40	100	50
Respiration Rate	brpm	>32	<8	50	NA
Systolic Blood Pressure (supine)	mmHg	>200	<85	60	20
Diastolic Blood pressure (supine)	mmHg	>120	<40		0.2x

\*Pre-dose values will be used for corresponding post-dose values assessment at TV1. Otherwise baseline values are used.

Orthostatic hypotension will be defined as a reduction in SBP of 20 mmHg or more, and/or a reduction in DBP of 10 mmHg or more, for the standing measurement compared to the supine/semi-supine measurement.

### 9.7. ELECTROCARDIOGRAM

Standard 12-lead ECGs will be obtained after the patient has rested in a supine position for at least 5 minutes. Electrocardiograms will be measured using an ECG machine that automatically calculates the HR and measures PR, QRS, QT, QT interval corrected using Bazett's formula (QTcB) and QT interval corrected using Fridericia's formula (QTcF).

The following will be summarized:

- Change from baseline to other visit pre-dose values for each parameter. Baseline is defined as the last non-missing assessment before the first dose of CVT-301 in study CVT-301-004 for the patients who received CVT-301 in CVT-301-004 and as the last non-missing assessment before the first dose of CVT-301 in CVT-301-004E for the rest of the patients. '.

## Statistical Analysis Plan

- Number and percentage of patients with PCS values at each applicable visit for each parameter
- Number and percentage of patients with PCSC values at each applicable visit for each parameter

PCS and PCSC will be identified as outlined in the following table.

ECG	Units	Criteria for PCS Values (Actual values)		Criteria for PCSC values (Change from Baseline)	
		High	Low	increase	decrease
PR interval	msec	>300	NA	>25% for baseline $\geq$ 200 >50% for baseline <200	NA
QRS interval	msec	>200	NA	>25% for baseline $\geq$ 100 >50% for baseline <100	NA
QTcB	msec	>500	NA	>15% for baseline $\geq$ 440 >30% for baseline <440 >30 msec increase >60 msec increase Change>30 and value>500 Change>60 and value>500	NA
QTcF	msec	>500	NA	>15% for baseline $\geq$ 440 >30% for baseline <440 >30 msec increase >60 msec increase Change>30 and value>500 Change>60 and value>500	NA
Heart Rate	bpm	>120	<35	NA	NA

### 9.8. PHYSICAL EXAMINATION

A complete physical examination (head, eyes, ears, nose, and throat [HEENT], heart, lungs, abdomen, skin, cervical and axillary lymph nodes, neurological, and musculoskeletal systems) will be performed at screening. Genital, rectal, and breast examination may be excluded if not clinically indicated.

The following will be summarized:

- Total number and percentage of patients reporting abnormal clinically significant physical examination results

### 9.9. COLUMBIA-SUICIDALITY SEVERITY RATING SCALE

The C-SSRS is a measure of suicidal ideation and behavior. The rating scale has 4 general categories: suicidal ideation, intensity of ideation, suicidal behavior, and actual

## Statistical Analysis Plan

attempts. All C-SSRS data will be listed. The frequency and percentage of patients with each response for suicidal ideation, intensity of ideation, and suicidal behavior items will be summarized as appropriate by treatment group and overall.

A shift table from baseline to each visit, days 1, 3, 6, 8, 11, 14, 17, 24, and 28 after LDOT will be constructed to assess any changes in the subjects' suicidal ideation and behavior during the treatment period.

A shift table from LDOT to days 1, 3, 6, 8, 11, 14, 17, 24, and 28 after TV6 will be constructed to assess any changes in the subjects' suicidal ideation and behavior during the treatment period.

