10.1.4. Sub-Study to Assess Potential Withdrawal Symptoms

After patients are consented to protocol Version 5.2, they will participate in a withdrawal symptom sub-study at the end of TV4, TV5, or TV6, depending on which of the visits is the next scheduled one for the patient. In addition to the assessments detailed in the previous sections for the treatment visit, the AWQ and DDS-PC will be performed upon arrival in the ON state, and the UPDRS Part 1 will be performed preferably in the ON state.

When study activities for the visit are completed, patients will begin a 28-day period of assessment of potential drug withdrawal symptoms. To this end, patients who are at TV4 or TV5 at the time of consent will go on a study drug holiday for this time period. All patients in the withdrawal sub-study (patients consented to protocol Version 5.2) will be given copies of the AWQ, the DDS-PC, PHQ-9, Epworth Sleepiness Scale, C-SSRS (self-report version), and the self-administered MDS-UPDRS Parts 1B and 2 (Movement Disorder Society -UPDRS) to be completed at home at 1, 3, 6, 8, 11, 14, 17, 24, and 28 days after the treatment visit. Patients should fill out the questionnaires during their first ON state (after the intake of their first scheduled dose of standard oral PD medication) on each of these days. The site will call patients

at 14 (± 3) days after the treatment visit to remind them to complete the questionnaires, and to inquire about potential adverse events and changes in concomitant medications. Patients who enter the withdrawal sub-study after TV6 will also receive a call at 28 (± 3) days.

Patients who entered the study drug holiday will be scheduled to return to the clinic for a drug re-supply visit (see [Section 10.1.4.1](#)), and resumption of the full course of study treatment. Patients who entered the withdrawal sub-study after TV6 will be completed with the study after they return the questionnaires and undergo the DLco and spirometry assessment 4 to 5 weeks after completion of TV6, as described in [Section 10.1.3.9](#).

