## Statistical Analysis Plan

patients. This summary will be complemented by the distribution of each response category (much improved, improved, a little improved, no change, a little worse, worse, much worse) tabulated by the treatment group. The data will be summarized with descriptive statistics within each treatment group and overall.

- Changes from baseline in endpoints based on S&E ADL score, UPDRS Part 2 score, PHQ-9 total score, and PDQ-39 sub-scores and index score. An ANCOVA model with the treatment group, treatment/study group and stratification variables as fixed factors and the baseline value as a covariate will be used to estimate the treatment group differences. In addition, the data will be presented with descriptive statistics classified by treatment group and visit. The observed cases will be used in the analysis and summaries.
- Change from baseline (TV1) and Last Day of Treatment (LDOT) to days 1, 3, 6, 8, 11, 14, 17, 24, and 28 after TV6 in the PHQ-9 will be summarized descriptively. LDOT is defined as assessment taken on TV6 or ET for patients who didn't enrolled into the sub-study and TV4, TV5 or TV6 for patients who enrolled into sub-study.

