## Statistical Analysis Plan

Table 14.2.2.1.8	Efficacy Subgroup Analysis: Change from Baseline in Total Daily OFF Time by Treatment Group, Visit and Age Group (ITT Population)
Table 14.2.2.1.9	Efficacy Subgroup Analysis: Change from Baseline in Total Daily OFF Time by Treatment Group, Visit and Gender (ITT Population)
Table 14.2.2.2.1	Efficacy Analysis: Mean of Total Daily ON Time without Dyskinesia by Treatment Group and Visit (ITT Population)
Table 14.2.2.3.1	Efficacy Analysis: Mean of Total Daily ON Time with non-Troublesome Dyskinesia by Treatment Group and Visit (ITT Population)
Table 14.2.2.4.1	Efficacy Analysis: Mean of Total Daily ON Time with Troublesome Dyskinesia by Treatment Group and Visit (ITT Population)
Table 14.2.3.1	Efficacy Analysis: Subjects Global Impression of Change (PGI-C) by Treatment Group and Visit Worst Case Imputation [a] (ITT Population)
Table 14.2.4.1	Efficacy Analysis: UPDRS Part 2 Score by Treatment Group and Visit (ITT Population)
Table 14.2.4.2	Efficacy Analysis: Schwab and England (S&E) Activities of Daily Living (ADL) Score by Treatment Group and Visit (ITT Population)
Table 14.2.4.3	Efficacy Analysis: 39 Item Parkinson's disease Questionnaire (PDQ-39) Sub-scores and Summary Index Score by Treatment Group, Visit (ITT Population)
Table 14.2.4.4	Efficacy Analysis: 9-Item PHQ-9 Sum Score by Treatment Group and Visit (ITT Population)
Table 14.2.4.4.1	Change from Baseline (TV1) and Last Day of Treatment (LDOT) to Days 1, 3, 6, 8, 11, 14, 17, 24, and 28 after LDOT in PHQ-9 Total Score by Treatment Group (ITT Population)
Table 14.2.4.5.1	Efficacy Analysis: Impact of Parkinson's OFF Episodes Patient Survey Score by Treatment Group and Visit (ITT Population)
Table 14.2.4.5.2	Exploratory Efficacy Analysis: Frequency of Impact of Parkinson's OFF Episodes Patient Survey by Treatment Group and Visit (ITT Population)
Table 14.3.1.1.1	Extent of Exposure: Overall Exposure by Treatment Group (Safety Population)
Table 14.3.1.1.2	Extent of Exposure: Overall Exposure by Treatment/Study (ITT Population)
Table 14.3.1.2.1	In-Clinic Study Drug Administration by Treatment Group (Safety Population)
Table 14.3.1.2.2	In-Clinic Study Drug Administration by Treatment/Study (ITT Population)
Table 14.3.1.3.1	Distribution of Time of Study Drug Administration by Treatment Group (Safety Population)
Table 14.3.1.3.2	Distribution of Time of Study Drug Administration by Treatment/Study (ITT Population)

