## Statistical Analysis Plan

Table 14.3.4.5.11.2	Summary of Spirometry(Neurology Office):Categories of Change from Baseline for FEV1 and FVC by Treatment/Study and Visit (Safety Population)
Table 14.3.4.5.11.3	Summary of Spirometry(Neurology Office):Categories of Change from Baseline for FEV1 by Treatment Group, Visit and Smoker Status (Safety Population)
Table 14.3.4.5.11.4	Summary of Spirometry(Neurology Office):Categories of Change from Baseline for FEV1 by Treatment/Study, Visit and Smoker Status(Safety Population)
Table 14.3.4.5.12.1	Summary of Spirometry(Neurology Office):Categories of Change from Baseline for FEV1/FVC by Treatment Group and Visit (Safety Population)
Table 14.3.4.5.12.2	Summary of Spirometry(Neurology Office):Categories of Change from Baseline for FEV1/FVC by Treatment/Study and Visit (Safety Population)
Table 14.3.4.5.13.1	Summary of Spirometry (Neurology Office): Actual Values and Change from Pre-dose for FEV1 and FVC at TV1 (Safety Population)
Table 14.3.4.5.13.2	Summary of Spirometry (Neurology Office): Actual Values and Change from Pre-dose for FEV1/FVC at TV1 (Safety Population)
Table 14.3.4.5.13.3	Summary of Spirometry (Neurology Office): Actual Values and Change from Pre-dose for FEV1 at TV1 by Smoker Status (Safety Population)
Table 14.3.4.5.14.1	Summary of Spirometry (Neurology Office): Categories of Percent Change from Pre-dose for FEV1, FVC at TV1 (Safety Population)
Table 14.3.4.5.14.2	Summary of Spirometry (Neurology Office): Categories of Percent Change from Pre-dose for FEV1/FVC at TV1 (Safety Population)
Table 14.3.4.5.14.3	Summary of Spirometry (Neurology Office): Categories of Percent Change from Pre-dose for FEV1 at TV1 by Smoker Status (Safety Population)
Table 14.3.4.6.1	Summary of Columbia-Suicide Severity Rating Scale (C-SSRS) by Treatment Group and Visit (Safety Population)
Table 14.3.4.6.2	Shift from Baseline in Columbia-Suicide Severity Rating Scale (C-SSRS) by Treatment Group and Visit (Safety Population)
Table 14.3.4.6.3	Summary of Self-Reported Columbia-Suicide Severity Rating Scale (C-SSRS) by Treatment Group and Visit (Safety Population)
Table 14.3.4.7	Summary of Epworth Sleepiness Scale Total Score: Actual Values and Change from Baseline by Treatment Group and Visit (Safety Population)

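### The C-SSRS shift table from LDOT (SAP 9.9) and the PHQ-9 withdrawal text (SAP 8.1) count days after TV6 instead of after LDOT; read literally, both omit patients whose drug holiday follows TV4 or TV5

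*SAP*

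**What the plan says.** The withdrawal sub-study (Protocol 10.1.4) starts at whichever of TV4, TV5 or TV6 is the patient's next visit after consent to Version 5.2. For the earlier entrants, "patients who are at TV4 or TV5 at the time of consent will go on a study drug holiday for this time period". Home questionnaires, including PHQ-9 and the self-report C-SSRS, are completed on nine days from Day 1 to Day 28 after that visit. Holiday patients are then resupplied and resume study drug.

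SAP 9.9 plans two C-SSRS shift tables. The first is "A shift table from baseline to each visit, days 1, 3, 6, 8, 11, 14, 17, 24, and 28 after LDOT". The second is "A shift table from LDOT to days 1, 3, 6, 8, 11, 14, 17, 24, and 28 after TV6".

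For PHQ-9, SAP 8.1 plans "Change from baseline (TV1) and Last Day of Treatment (LDOT) to days 1, 3, 6, 8, 11, 14, 17, 24, and 28 after TV6". The same bullet defines LDOT as "TV4, TV5 or TV6 for patients who enrolled into sub-study". The matching output in SAP 14, Table 14.2.4.4.1, is titled with days "after LDOT in PHQ-9 Total Score by Treatment Group (ITT Population").

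**The concern.** The sub-study is there to find symptoms that appear when the drug is stopped. For each patient the relevant contrast runs from the last on-drug assessment to the days that follow it. The SAP plans that contrast for C-SSRS and PHQ-9, but dates the off-drug days from TV6. For a patient on holiday after TV4 or TV5, the starting point is then TV4 or TV5 and the end points are days on which no withdrawal forms exist. A programmer who follows the text would produce tables holding only patients whose withdrawal period begins at TV6, and nothing in the output would show that the holiday patients had been left out. Suicidal ideation and depression are among the more serious symptoms these forms could pick up.

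**Working it through.** The plan gives no figure to reproduce. The check compares the anchors and then tests whether any holiday form could fall after TV6.

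**Anchors side by side**

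| Analysis | Place in SAP | Days counted from |
|---|---|---|
| C-SSRS shift from baseline | 9.9, first shift table | LDOT |
| C-SSRS shift from LDOT | 9.9, second shift table | **TV6** |
| PHQ-9 change from baseline and from LDOT | 8.1, text | **TV6** |
| PHQ-9, same analysis | 14, Table 14.2.4.4.1 | LDOT |
| Epworth | 9.10; Table 14.3.4.7.1 | LDOT |
| AWQ | 9.14; Table 14.3.4.11 | LDOT |
| DDS-PC | 9.15; Table 14.3.4.12 | LDOT |
| MDS-UPDRS | 9.16; Tables 14.3.4.13.1 and 14.3.4.13.2 | LDOT |

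**Timing.** Inputs: TV4 at day 168 ± 14, TV5 at day 252 ± 14 and TV6 at day 364 ± 14 (SAP 3.8); TV6 at 56 ± 2 or 60 ± 2 weeks (Protocol 10.1.3.9); last home form on Day 28 (Protocol 10.1.4).

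Latest holiday form = visit day + window + 28:
- after TV4: 168 + 14 + 28 = day 210
- after TV5: 252 + 14 + 28 = day 294

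Earliest TV6 = visit day − window:
- SAP, week 52: 364 − 14 = day 350
- Protocol, week 56: 392 − 14 = day 378
- Protocol, week 60: 420 − 14 = day 406

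The smallest gap is 350 − 294 = 56 days, so 0 of the 9 holiday forms can fall after TV6. The order does not depend on the windows: Protocol 10.1.4.1 collects the completed forms at TV4.1 or TV5.1. Footnote 4 of Appendix 10 gives post-TV6 forms only to patients whose withdrawal period begins at that visit, so holiday patients do not generate a second set.

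**Where holiday patients remain.** They stay in the baseline C-SSRS shift, in the self-report C-SSRS summary (Table 14.3.4.6.3, Safety Population, no TV6 restriction) and in the C-SSRS and PHQ-9 listings. They also stay in the PHQ-9 table if its title is followed and not the text.

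**Table index.** The C-SSRS entries are 14.3.4.6.1 to 14.3.4.6.3: a summary, the "Shift from Baseline in Columbia-Suicide Severity Rating Scale (C-SSRS) by Treatment Group and Visit (Safety Population"), and the self-report summary. No entry corresponds to the shift from LDOT, whereas PHQ-9, Epworth, AWQ and DDS-PC each have a table of change from LDOT.

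**The case against.** The strongest reply is that this is a drafting slip which the rest of the SAP corrects. The PHQ-9 bullet defines LDOT to include TV4 and TV5, which would be pointless if only TV6 entrants counted. No table title carries the TV6 anchor. Protocol 12.5 describes the analysis over the withdrawal assessment period without restricting it to TV6, and SAP 11 declares no such change. The summaries are descriptive, so no test and no primary endpoint is affected.

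Most of that stands. For PHQ-9 the defect is a conflict between text and table title, and exclusion follows only if the text is programmed. For the C-SSRS shift from LDOT, however, no title exists to correct the text, because the table is missing from the index. The baseline shift is not a substitute. Its baseline precedes the first dose of CVT-301, which for patients treated in CVT-301-004 lies in the parent study (SAP 6.2). It therefore mixes change on treatment with change after stopping. Protocol 12.3 itself exempts withdrawal assessments from the usual baseline. The self-report summary gives frequencies, not within-patient change. Finally, the SAP states that it supersedes the protocol (SAP 2), and the second interim analysis is to be run on this SAP (SAP 10), so its literal wording matters.

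**Conclusion.** Wrong as written, in two places: the second C-SSRS shift table in SAP 9.9 and the PHQ-9 withdrawal text in SAP 8.1. Each patient with a holiday after TV4 or TV5 contributes 0 of 9 home assessments to those two analyses as worded. The share of patients this concerns cannot be computed, because neither document says how many entered at each visit. The conclusion assumes that visits keep the protocol order and that the early withdrawal visit stands in for TV6.

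Two stronger inferences are not supported. A reader might infer that holiday patients vanish from the suicidality and depression withdrawal results altogether. They do not: the baseline C-SSRS shift, the self-report summary and the listings keep them, and the PHQ-9 table title would too. A reader might also argue that a smaller denominator widens a rule-of-three upper limit on suicidal ideation. That limit concerns an event looked for and not seen in the patients observed. Events during a holiday would still appear in the outputs just named, so the number of patients observed for ideation does not shrink.

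**What to change.** 1. In SAP 8.1 (PHQ-9), count the withdrawal days from LDOT instead of TV6, which brings the text into line with Table 14.2.4.4.1.
2. In SAP 9.9, make the same replacement in the second C-SSRS shift table.
3. Add to SAP 14 a table for the C-SSRS shift from LDOT, Days 1–28 after LDOT, by treatment group, Safety Population.

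The cost is two phrases and one table shell. The forms are already collected, and no visit, dose or clinical rule changes. The wording should be settled before the analyses under this SAP are programmed.
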